#### 9.4.2 ANALYSIS OF THE PRIMARY ENDPOINT(S)

Questions	Defined/explained
Primary endpoint	
Describe how the primary endpoint is calculated, if not readily apparent	Change in Overdose Admissions: Using electronic health records, it is calculated as the total combined number of overdoses resulting in an emergency department presentation within the specified time period.
Describe the scale (nominal/binary/categorical, ordinal, interval); state if it is measured as a single endpoint/summary measure or repeated measure	binary
Describe the statistical procedure(s) that will be used to analyze the primary endpoint (e.g., multiple regression, repeated measures mixed models, logistic regression, Analysis of Covariance (ANCOVA)). Describe the covariates and factors in the model. Provide a rationale for covariates and how they will be selected to achieve a parsimonious model. If the decision to specify covariates is deferred for the SAP, indicate here.	Summarized using frequencies and percentages and then compare arms using the Fisher's exact test.
Describe how results of statistical procedure(s) will be presented (e.g., adjusted means (Least-squares means (LSMEANS)) with standard errors, odds ratios with 95% confidence intervals, prevalence rates, number-needed-to-treat)	Presented using frequencies and percentages
Describe details to check assumptions required for certain types of analyses (e.g., proportional hazards, transformations or, when appropriate, nonparametric tests)	The nonparametric Fisher's exact test is used to compare the primary endpoint.
Describe the Populations for which the analysis will be conducted, as discussed in Section 9.3, Populations for Analyses	All study participants
Describe how missing data will be handled (e.g., type of imputation technique, if any, and provide justification), and approach to handling outliers, non-adherence and lost to follow-up	We do not expect there to be a large amount of missing data due to the use of administrative datasets. However, missing values may occur when subjects die during the specified time period. Sensitivity analysis is performed by excluding subjects who die during the specified time period.

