## 9 STATISTICAL CONSIDERATIONS

## 9.1 STATISTICAL HYPOTHESES

Primary Endpoint:

- Overdose Admissions
  - [Measured: 1 year pre-enrollment through 1 year post-enrollment]

We hypothesize that, compared to patients in the control condition, patients receiving the POINT intervention will experience fewer subsequent admissions to the ED for overdose.

Secondary Endpoints:

- MOUD Engagement
  - [Measured: 1 year pre-enrollment through 1 year post-enrollment]
- Duration of MOUD Engagement
  - [Measured: 1 year pre-enrollment through 1 year post-enrollment]
- ED Admissions
  - [Measured: 1 year pre-enrollment through 1 year post-enrollment]
- Inpatient Hospital Admissions
  - [Measured: 1 year pre-enrollment through 1 year post-enrollment]
- Time to Relapse
  - [Measured: Enrollment through 1 year post-enrollment]
- Medicaid Enrollment for Participants Without Insurance
  - [Measured: Enrollment through 1 year post-enrollment]
- Child Welfare Involvement
  - [Measured: 3 years pre-enrollment through 1 year post-enrollment]
- Incarceration
  - [Measured: 3 years pre-enrollment through 1 year post-enrollment]

We hypothesize that, compared to patients in the control condition, patients receiving the POINT intervention will experience better recovery outcomes (i.e., higher MOUD engagement and longer duration of engagement, lower ED and inpatient admissions, longer times between relapse, higher Medicaid enrollment for those without insurance, lower child welfare involvement, and lower incarceration).

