## 9.2 SAMPLE SIZE DETERMINATION

Our goal is to obtain a total of 356 patients in each study arm ( $n = 712$ ) by Month 32, which will provide us with enough patients to obtain a full year of follow-up data to detect a minimum 6% reduction in our primary outcome (subsequent overdose) at 80% power, assuming a 12% rate of subsequent overdose for the standard care arm at the 5% significance level (this is a conservative calculation based on observed subsequent overdose rates at Eskenazi and Indianapolis Emergency Medical Services).

(Note: This goal was not ultimately reached due research activities needed to stop because of the COVID-19 pandemic. Researchers developed an alternative plan to assess outcomes using a retrospective case control design that was approved by the funder. However, all planned analyses were conducted using data collected from patients who were enrolled in the trial.)

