### 9.4 STATISTICAL ANALYSES

#### 9.4.1 GENERAL APPROACH

We will summarize patient characteristics using means and standard deviations for continuous variables and counts and proportions for categorical variables. Initial analysis of outcomes (using data pulled at 9 months) will focus on MOUD engagement one-month post overdose, as all other outcomes will be too distal to observe any meaningful change. This time period is based on our prior POINT experience demonstrating initial engagement tends to happen within 1-2 weeks of overdose. We will focus on immediate outcomes (e.g., treatment engagement, length, dropout). While observed change in more distal outcomes (e.g., subsequent overdose and mortality) is unlikely to be seen in such a short pilot period, we will look at them and, if needed, adjust the benchmark (established based on our experience at Eskenazi) for the power analysis. Summary of outcome measures will be computed similarly. The 95% confidence intervals of outcome measures for the POINT and standard care arms will be used to estimate the rate of binary outcomes and mean of continuous outcomes.

The primary analysis involves comparison of outcome measures post ED discharge between the POINT and standard care arms. Binary outcome measures (e.g., MOUD engagement and dropout, subsequent overdose, overdose mortality, and all-cause mortality) will be compared between the POINT and standard care arms using the Fisher's exact test. Length of MOUD treatment will be compared using the Wilcoxon rank sum test. Comparison of the length of time to relapse will be conducted using the survival analysis. Time to relapse will be plotted using the Kaplan Meier curve and comparison between the POINT and standard care arms will be performed using the log rank test.

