The secondary analysis involves comparing outcome measures pre- and post-ED discharge for POINT patients. Binary outcomes including child welfare involvement will be compared using the McNemar's test and the continuous outcome including the days of incarceration will be compared using the Wilcoxon signed rank test due to the skewness of the data. Additional analyses will be conducted to account for patient characteristics in the comparison between the POINT and standard care arms using logistic regression for binary outcomes, Poisson regression for length of MOUD treatment, and Cox proportional hazards model for time to relapse. For the comparison pre- and post-ED discharge in the POINT arm, generalized estimating equations approach will be performed using logistic regression for Medicaid enrollment and child welfare involvement and Poisson regression for days of incarceration. Hospitals will be included in the models as a fixed effect to account for the potential differences in patient population across hospitals.

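### The primary and four secondary endpoints are defined over a window that includes the year before enrollment, which contradicts the planned post-discharge comparison; inpatient stays running on from the index visit have no rule

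*Combined protocol and SAP*

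**What the plan says.** Section 9.1 attaches the same bracket, "Measured: 1 year pre-enrollment through 1 year post-enrollment", to five endpoints: overdose admissions (the primary), MOUD engagement, MOUD duration, ED admissions and inpatient admissions. Time to relapse and Medicaid enrollment instead have "Measured: Enrollment through 1 year post-enrollment". Child welfare involvement and incarceration run from three years before to one year after enrollment.

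Section 9.4.2 names the primary as a *Change* and then defines it: "it is calculated as the total combined number of overdoses resulting in an emergency department presentation within the specified time period". It calls the result binary and assigns Fisher's exact test. Section 9.4.3 treats the other four in the same way. ED and inpatient admissions are all-cause totals classed as binary, MOUD engagement is any episode, and MOUD duration is a number of days, each over the endpoint's stated period. None of the five definitions subtracts a pre-period value or excludes the index visit.

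Other text looks only forward. The primary hypothesis is that "patients receiving the POINT intervention will experience fewer subsequent admissions to the ED for overdose". Section 9.2 sizes the trial to "detect a minimum 6% reduction in our primary outcome (subsequent overdose) at 80% power", with a full year of follow-up. Section 9.4.1 states: "The primary analysis involves comparison of outcome measures post ED discharge between the POINT and standard care arms", and 9.4.3 repeats this. Section 9.4.1 also gives pre-enrollment data a separate use: "The secondary analysis involves comparing outcome measures pre- and post-ED discharge for POINT patients".

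Section 8.1 allows enrollment of patients who leave the ED for an inpatient bed as well as those going home.

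**The concern.** The definitions and the comparison cannot both be applied as written. A programmer who takes the period from 9.1 and the calculation from 9.4.2 and 9.4.3 would pool the pre-enrollment year, the index visit and the follow-up year into one indicator. Neither the earlier year nor the index visit can be affected by the intervention, so anyone positive there contributes nothing to the contrast.

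The inpatient endpoint has a further gap that the post-discharge reading does not close. A stay that starts as the patient leaves the ED can be dated at or after ED discharge, and no section says whether it is an outcome or part of the index episode.

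This matters beyond drafting because 9.2 reports that "all planned analyses were conducted using data collected from patients who were enrolled in the trial". The definition actually programmed should therefore be stated with the results.

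**Working it through.** **1. The plan's own figure.** Inputs from 9.2: 12% in standard care, a 6% reduction (taken as 12% to 6%), 80% power, 5% significance. Sidedness is not stated; two-sided is assumed. With the pooled-variance formula, no continuity correction and a mean rate of 0.09:

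n = [1.960·√(2·0.09·0.91) + 0.842·√(0.12·0.88 + 0.06·0.94)]² / 0.06² = [0.793 + 0.339]² / 0.0036 ≈ 355.9, so 356 per arm.

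This matches 9.2 exactly, with power 80.0% (77.1% for Fisher's test by exact enumeration). The planned size therefore belongs to subsequent overdose at 12% versus 6%.

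**2. Post-discharge reading.** The rates stay at 12% and 6%, so n stays at 356 and power at 80.0%. Nothing is lost.

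**3. Literal reading of all-cause ED admissions.** Under 5.5 and 8.1, consent follows clearance for discharge, so every index ED presentation precedes enrollment and falls inside the window. Each participant has at least one presentation, and the binary endpoint is 100% in both arms. This needs no assumption.

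**4. Literal reading of MOUD.** Any episode in the year before enrollment makes a participant engaged, and prior-year treatment days add to duration.

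**5. Literal reading of the primary, illustration only.** Let q be the share already positive through a prior-year or index overdose. Inclusion criterion 1 in 5.1 allows the index visit to be an overdose. The documents do not give q; it is assumed equal in both arms and independent of later risk. The rates become q + (1−q)·0.12 and q + (1−q)·0.06, so the difference is 0.06·(1−q).

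| q | Standard care | POINT | Difference | Power at 356 per arm |
|---|---|---|---|---|
| 0 | 12.0% | 6.0% | 6.0 points | 80.0% |
| 10% | 20.8% | 15.4% | 5.4 points | 46.5% |
| 20% | 29.6% | 24.8% | 4.8 points | 30.1% |
| 30% | 38.4% | 34.2% | 4.2 points | 21.3% |
| 50% | 56.0% | 53.0% | 3.0 points | 12.4% |

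Power is by normal approximation. Section 9.2 says planned enrollment was not reached and does not give the achieved number.

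**6. Inpatient admissions, post-discharge reading.** Let s be the share admitted directly from the index visit (not in the documents; assumed equal in both arms), with each such stay recorded as a post-discharge admission. For later admission rates c and t, the observed rates are s + (1−s)·c and s + (1−s)·t, so a true difference d becomes d·(1−s). An assumed difference of 10 points would become 9 points at s = 10% and 8 points at s = 20%.

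**The case against.** The strongest reply is that the window is already settled. Sections 9.4.1 and 9.4.3 both place the between-arm comparison after ED discharge and list subsequent overdose among the binary outcomes for Fisher's test; the hypothesis and sample size agree. The pre-enrollment year has a use in the pre/post comparison, so the bracket in 9.1 may simply describe the span of data collected. An ED endpoint fixed at 100% is itself a sign that the bracket was never meant as the outcome window.

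Most of this stands. It sets the severity and means that no power loss can be claimed for the primary on the reading the plan favors. It does not remove the contradiction. Section 9.1 has forward-only wording and uses it for time to relapse but not for the primary. Nor do the brackets follow the pre/post analysis: 9.4.1 plans a pre/post model for Medicaid enrollment, whose bracket has no pre-period, and none of the outcomes it names for pre/post analysis is among the five.

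Three stronger readings are tempting. A reader might infer that the pooled window was used and that the reported primary result is wrong; no section says so. A reader might infer that the plan gives no indication of which definition applies; 9.4.1 and 9.4.3 do give one. A reader might infer that direct inpatient stays favor one arm. Arms are allocated by randomized shift (6.3), and what can be shown is dilution of one secondary endpoint for which no power was planned. Even that depends on how the stay is dated, which the documents do not say.

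**Conclusion.** The inconsistency is real and involves the primary endpoint. It should be fixed, but it is not shown to have damaged the primary result. The mismatch of windows, and the 100% ED endpoint under the literal definition, follow from the text alone. The loss of power for the primary arises only under the literal reading, and its size rests on shares the documents do not give. On the post-discharge reading the loss is zero. The inpatient gap remains on either reading: if direct stays are recorded as post-discharge admissions, those patients are positive whatever POINT does, and the true difference shrinks by the factor 1−s, with s unknown.

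**What to change.** - In 9.1, 9.4.2 and 9.4.3, define the five between-arm outcomes as events, or MOUD days, after index-ED discharge through one year.
- Exclude the index visit explicitly and, for inpatient admissions, any stay that continues directly from it.
- Remove *Change* from the endpoint names.
- Say that the pre-enrollment year serves baseline description and the pre/post analysis in 9.4.1.
- State the post-discharge between-arm window for child welfare and incarceration too, since their brackets reach back three years.
- Keep Fisher's exact test and the sample-size basis.
- Report which definition the conducted analyses used. Re-derive outcomes only if the pooled window was used, and the inpatient outcome also if direct stays were counted.

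The cost is wording in three sections and one statement in the report. No new data collection is needed: the administrative data in 8.1 span three years before to two years after enrollment, and time to relapse already requires dated overdose visits.

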### 3 OBJECTIVES AND ENDPOINTS

OBJECTIVES	ENDPOINTS	JUSTIFICATION FOR ENDPOINTS	PUTATIVE MECHANISMS OF ACTION
Primary			
Assess POINT's effectiveness at reducing overdose presentations to the emergency department.	Overdose Admissions	The primary goal of the intervention as it is designed is to reduce overdoses by linking clients to MOUD treatment.	Engagement in MOUD treatment is demonstrated to reduce overdose.
Secondary			
Assess POINT's effectiveness at improving treatment-related outcomes.	MOUD Engagement Duration of MOUD Engagement Time to Relapse ED Admissions Hospital Admissions Overdose Mortality Medicaid Enrollment	These outcomes should improve following linkage to MOUD.	MOUD treatment is associated with better treatment outcomes compared to alternative treatments for OUD.
Exploratory			
Assess POINT's effectiveness at improving recovery-related outcomes.	Child Welfare System Involvement Incarceration	These outcomes should improve as a function of treatment engagement.	MOUD treatment should result in greater abstinence from illicit opioids that will improve other areas of a patient's life.

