#### 9.4.3 ANALYSIS OF THE SECONDARY ENDPOINT(S)

Secondary endpoints	
Note if analysis of secondary endpoint(s) are dependent on findings of primary endpoint	Analysis of secondary endpoints are not dependent on the findings of primary endpoint.
Describe how each secondary endpoint is calculated, if not readily apparent	
Change in MOUD Engagement: Using state methadone treatment data, Medicaid claims data, state prescription drug monitoring data, and electronic health records data to identify whether or not the person engaged in at least one episode of MOUD treatment (methadone, buprenorphine, or naltrexone) within the specified time period.
 
Change in MOUD Engagement Duration: Using state methadone treatment data, Medicaid claims data, state prescription drug monitoring data, and electronic health records data to calculate the number of days MOUD treatment was received during the specified time period.
 
Change in ED Admissions: Using electronic health records, it is calculated as the total combined number of all-cause ED presentation within the specified time period.
 
Change in Inpatient Hospital Admissions: Using electronic health records, it is calculated as the total combined number of all-cause hospital admissions within the specified time period.
 
Time to Relapse: Using electronic health records data, it is calculated as number of days to the first overdose ED visit or overdose death since the index ED. Subjects who did not experience overdose ED or overdose death are censored at the end of the specified time period or the time of death due to other reasons, whichever occurred first
 
Change in Medicaid Enrollment for Participants Without Insurance: Using Medicaid claims data to identify Medicaid coverage among participants within the specific time period.

	
Change in Child Welfare Involvement: Using child welfare data to identify the number of new cases and children removed from the home within the specified time period.
 
Change in Incarceration: Using public incarceration data to identify the number of days of incarceration within the specific time period.

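### The one named sensitivity analysis of the primary endpoint excludes everyone who dies, so it cannot test whether fatal overdoses outside the ED alter the primary comparison (minor)

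*Combined protocol and SAP*

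**What the plan says.** The primary objective in Section 3 is "reducing overdose presentations to the emergency department". Section 9.4.2 derives the endpoint from electronic health records as "the total combined number of overdoses resulting in an emergency department presentation within the specified time period", treats it as binary, and compares the arms by Fisher's exact test in all study participants. Section 9.3 likewise includes everyone who consented.

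The missing-data row of Section 9.4.2 expects little missing data but adds that "missing values may occur when subjects die during the specified time period". It then gives the only analysis that the documents call a sensitivity analysis: "Sensitivity analysis is performed by excluding subjects who die during the specified time period". No exception is made for a participant whose ED overdose was recorded before death, or for a death that was itself an overdose. The covariate-adjusted regressions in Section 9.4.1 are described as additional analyses.

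Fatal overdose is covered elsewhere:
- Section 9.4.1 lists "subsequent overdose, overdose mortality, and all-cause mortality" among the binary outcomes compared by arm.
- Section 9.4.3 defines Time to Relapse: "Using electronic health records data, it is calculated as number of days to the first overdose ED visit or overdose death". Participants without such an event are "censored at the end of the specified time period or the time of death due to other reasons", whichever came first. The window in Section 9.1 is "Measured: Enrollment through 1 year post-enrollment".
- Section 8.1 lists state vital records among the data obtained.

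**The concern.** Death happens after randomisation, and the plan itself compares it by arm, so a comparison restricted to survivors is no longer a comparison of the groups as randomised. Two further problems are specific to this endpoint.

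First, a participant with an ED overdose on record who later dies has an observed event. Exclusion deletes it as though it were missing.

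Second, someone who dies of an overdose without reaching an ED has no primary event, and exclusion then removes that person altogether. Whatever the death rate, the analysis counts none of these overdoses. If they fell unevenly between the arms, the ED-based comparison could give an incomplete picture of overdose, and the one check labelled for deaths would not show it. Conversely, the check can move away from the primary result merely because recorded events were dropped.

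**Working it through.** **Inputs.** Section 9.2 gives 356 per arm, 12% subsequent overdose under standard care, a 6% reduction (read as absolute, to 6%), 80% power and 5% significance. Every death count or death risk below is an assumption, because the documents give none.

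**The plan's own figure.** Two-sided, pooled variance under the null, no continuity correction, mean rate 0.09:

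n = [1.960·√(2·0.09·0.91) + 0.842·√(0.12·0.88 + 0.06·0.94)]² / 0.06² = 355.9, so 356 per arm. It reproduces and is not in dispute.

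**Reference result.** 0.12·356 = 42.7, taken as 43; 0.06·356 = 21.4, taken as 21. The difference is 43/356 − 21/356 = 12.08% − 5.90% = 6.18 points, Fisher p=0.0056.

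**Step 1: effect of dropping recorded events.** Let d₁ be the death risk among participants with an ED overdose and d₀ the risk among those without, each the same in both arms. After exclusion the rate in an arm with x events is

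x(1−d₁) / [x(1−d₁) + (356−x)(1−d₀)].

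| d₁ | d₀ | Control | POINT | Difference (points) |
|---|---|---|---|---|
| 10% | 2% | 38.7/345.44 = 11.20% | 18.9/347.20 = 5.44% | 5.76 |
| 5% | 5% | 40.85/338.20 = 12.08% | 19.95/338.20 = 5.90% | 6.18 |
| 5% | 10% | 40.85/322.55 = 12.66% | 19.95/321.45 = 6.21% | 6.46 |

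With death risks common to the arms, exclusion lowers the difference only when those with an ED overdose die at the higher rate. Equal risks leave it unchanged, and the reverse order raises it.

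If only ED-overdose cases die, at about 15% (6 control, 3 POINT), the result is 37/350 − 18/353 = 5.47 points, p=0.0075. The relative risk barely changes: 0.488 before, 0.482 after. If the deaths fall on one arm (6 control, 0 POINT), it is 37/350 − 21/356 = 4.67 points, p=0.028.

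**Step 2: fatal overdoses outside the ED.** These people have no primary event. Exclusion reduces the denominator; the composite keeps 356 and adds the deaths as events.

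| Deaths, control/POINT | Exclusion | Difference | ED overdose or overdose death | Difference | p |
|---|---|---|---|---|---|
| 0/6 | 43/356 vs 21/350 | 6.08 | 43 vs 27 | 4.49 | 0.058 |
| 0/5 | 43/356 vs 21/351 | 6.10 | 43 vs 26 | 4.78 | 0.042 |
| 2/4 | 43/354 vs 21/352 | 6.18 | 45 vs 25 | 5.62 | 0.016 |
| 3/3 | 43/353 vs 21/353 | 6.23 | 46 vs 24 | 6.18 | 0.0078 |
| 4/2 | 43/352 vs 21/354 | 6.28 | 47 vs 23 | 6.74 | 0.0035 |
| 6/0 | 43/350 vs 21/356 | 6.39 | 49 vs 21 | 7.87 | 0.0006 |

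From 0/6 to 6/0 the exclusion result moves 6.39 − 6.08 = 0.31 points, while the composite moves 7.87 − 4.49 = 3.38 points. Exclusion hardly responds to the imbalance. Only the extreme 0/6 split takes the composite past 0.05.

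**Step 3: what the other planned analyses would show.** The separate overdose-mortality test gives p=0.031 at 0/6 but p=0.22 at 1/5. With overdose deaths counted and event times assumed uniform over the year, the Time to Relapse log-rank test gives a median p of 0.044 at 0/6 and 0.0004 at 6/0, so it follows the composite.

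**Step 4: coding of deaths.** In the 0/6 case, keeping people who died without an ED overdose as non-events gives 6.18 points and treating them as missing gives 6.08. The coding rule alone is worth about 0.1 point.

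**The case against.** The exclusion sits in the missing-data row and addresses one question: whether incomplete observation after death affects the result. The endpoint is overdose presenting to an ED, so a fatal overdose elsewhere is not an endpoint event, and the check was never asked to find one. The main analysis keeps everyone, and Time to Relapse is already close to the proposed composite. Nearly all of this stands, and it is why the point is minor. What remains is that conditioning on death is a poor way to answer even the missing-data question, since a recorded ED overdose is not missing, and that no analysis designated as a check on the primary result counts the fatal events.

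Three stronger readings are tempting, and the documents do not support them:

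- A reader might infer that the plan ignores fatal overdoses. It does not: Time to Relapse and the mortality comparisons register them.
- A reader might infer that exclusion necessarily shrinks the treatment difference. Step 1 shows that this depends on who dies, which the documents do not say.
- A reader might infer that Time to Relapse also misses deaths outside the ED, because its definition names only electronic health records. That reading is strained: the definition expressly counts overdose death, Section 8.1 obtains vital records, and Sections 2.3.3 and 10.1.3 describe linking hospital and government data. Naming the source is a wording clarification.

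**Conclusion.** The point holds as a minor one. The only labelled sensitivity analysis of the primary endpoint conditions on a post-randomisation outcome, discards any ED overdose recorded for someone who later dies, and cannot show whether fatal overdoses outside the ED alter the comparison. The primary result itself is not affected.

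Size and direction in this trial are unknown. At the planned numbers and under assumed deaths, exclusion gave 5.8 to 6.5 points against 6.18 when death risks were common to the arms. With 0/6 non-ED overdose deaths it gave 6.1 points where counting them gave 4.5. Balanced deaths changed little, and only the 0/6 extreme lost significance. Section 9.2 reports that planned enrolment was not reached, so each death would carry more weight in the smaller sample.

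**What to change.** - Keep the primary endpoint and all consented participants. State that a death without a recorded ED overdose is coded as no ED overdose.
- Add, as the death-related sensitivity analysis, a Fisher's exact test of ED overdose or overdose death within 1 year of enrollment in all consented participants, using vital records and a stated rule for classing a death as an overdose.
- Name vital records as a source for Time to Relapse, and cross-refer to that endpoint as supporting the primary result.
- Section 9.2 describes the planned analyses as already conducted. If outcome data have been seen, still report the exclude-deaths result as planned and label the composite supplementary.

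The cost is one further test and a few lines of text. The primary endpoint and its power basis do not change. The drawbacks are a second data source, a cause-of-death rule and overlap with Time to Relapse, so the gain is a direct check on the primary result rather than much new information.
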